18.5 Disease Progression

The following are outcomes for the trial and will be recorded on the case report form and should not be reported separately on a SAE form:

- Disease progression
- Death due to disease progression
- Cancer recurrence

18.6 Assessment of SAEs by the Principal Investigator (or delegate)

The Principal Investigator (or delegated individual) is responsible for assessing all reported serious adverse events for reason for seriousness, causality and expectedness.

18.6.1 Relatedness/causality assessment

The assessment of "relatedness" to the study intervention is the responsibility of the PI at site, or an agreed designee.

All AEs judged as having a reasonable suspected causal relationship to the study intervention/procedure(s) are considered to be adverse reactions/responses. The assessment of relatedness is made using the following:

Relationship to intervention	Attribution (Causality)	Description
Unrelated	Unrelated	The AE is clearly NOT related to the intervention
	Unlikely	The AE is doubtfully related to the intervention
Related	Possible	The AE may be related to the intervention
	Probable	The AE is likely related to the intervention
	Definite	The AE is clearly related to the intervention

18.6.2 Expectedness

The Principal Investigator (or delegated individual) is responsible for assessing all serious adverse events for reason for causality. Only serious adverse events considered by the site investigator to be related (possibly, probably or definitely) to any of the study procedures should be reported to the CI or nominated person (NP) in the CTU. Such events must be reported within 24 hours to the central study team using the SAE form within the REDCap study database.

Assessment of expectedness will be made by the CI or NP. An unexpected event is not expected for the study intervention and is not listed in the treatment complications below. If in doubt, the CI will raise queries with the treating medical practitioner.

Related SAEs, which are in the opinion of the nominated person are considered unexpected for the study procedure will be submitted to the REC within 15 days of the CI/CTU becoming aware of the event, using the HRA report of serious adverse event form.

All intervention/study procedure-related SAEs will be recorded and reported to the REC as part of the annual reports.

18.7 Assessment of SAEs by the Chief Investigator

The CI shall be informed immediately of any SAEs via an automatic database alerting both to the SAE report. The CI shall assess the information in conjunction with any treating medical practitioners and confirm causality and expectedness. If in doubt, the CI will raise queries with the treating medical practitioner.

All intervention/study procedure-related SAEs will be recorded and reported to the REC as part of the annual reports. Unexpected SAEs related to the intervention/study procedures will be reported within the timeframes to the REC as stated below.

18.8 Reporting of unexpected SAEs to the Research Ethics Committee (REC)

All SAEs that are considered by the reporting Investigator or the Nominated Person to be related (i.e. resulted from administration of any of the research procedures) and unexpected (that is, the type of event is not expected for the study intervention) will be submitted to the REC within 15 days of the CI becoming aware of the event, using the HRA report of serious adverse event form.

18.9 Follow-up of Serious Adverse Events

A follow-up report must be completed when the SAE resolves, is unlikely to change, or when additional information becomes available. Follow-up information must also be provided as requested by the study office.

19 STATISTICAL CONSIDERATIONS

19.1 Statistical Analysis Plan (SAP)

The statistical aspects of the study are summarised here, with details fully described in a statistical analysis plan (SAP) that will be drafted early in the study and finalised prior to the final analysis data lock, or any planned interim comparative analyses. The SAP will be written by the Study Statistician in accordance with the current OCTRU SOPs. The SAP will be reviewed and will receive input from the Trial Steering Committee (TSC) and independent Data and Safety Monitoring Committee (DSMC).

19.2 Sample Size/Power calculations

We aim to recruit a total of 800 patients over 5 years from multiple NHS centres with the appropriate skill mix and expertise. Available data indicate that approximately 15% to 25% of men with intermediate-risk PCa undergoing RP or RRT will demonstrate treatment failure (i.e. clinical or biochemical relapse) within 5 years, with most failures occurring in the first 3 years. At our final analysis, when we should have approximately 3 years median follow-up, we estimate that about 10%

PART_Protocol_V3.0_15May2024_Clean.docx Page **54** of **77**

of men undergoing radical treatment will demonstrate treatment failure. It is hypothesised that radical treatment may be superior to PA in terms of oncological efficacy, but that radical treatment is considerably inferior to PA in terms of functional outcomes. The anticipated worse HRQoL with radical treatment compared with PA, in particular functional outcomes such as urinary continence, erectile function, and bowel toxicity, leads us to consider that radical treatment would need to achieve a 10% lower primary treatment failure rate (e.g. 10% compared to 20%) for it to remain the preferable option in clinical practice. This study is therefore a superiority trial, with treatment failure, and HRQoL and functional outcomes, hypothesised to be superior for PA versus radical treatment. Allowing for a 10% total dropout rate across the entire study, 800 patients randomised on a 1:1 basis to radical treatment or PA would provide approximately 88% power at p < 0.025 to detect a $\geq 10\%$ lower treatment failure rate (10% versus 20%, a hazard ratio of $0.4722 = \log(0.9)/\log(0.8)$) with radical treatment compared to PA treatment. The statistical power would not be much affected if the failure rate in the radical treatment group was somewhat lower, or somewhat higher, than 15%. For example, 800 patients (with 10% dropout) would provide approximately 79% power at p<0.025 to detect a difference of 15% versus 25% in failure rates (hazard ratio 0.5649 = log(0.85)/log(0.75)) and over 95% power to detect a 5% versus 15% failure rate (hazard ratio 0.3156 = log(0.95)/log(0.85)). With 800 patients randomised (and 10% lost to follow-up in total across the study), numerous sample size calculations using various parameters indicate that there will be ample statistical power to detect any meaningful differences in HRQoL scores, e.g. over 90% power at p<0.01 to detect a small to moderate (0.3sd) effect size. Put in perspective, this is a considerably smaller effect size than the 0.5sd effect size described by Norman et al (37) as the minimally important difference for HRQoL differences.

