The primary analysis is planned in the final six-months of the seven-year study, at which point median follow-up (from randomisation) will be approximately 3 years. To allow for having two co-primary outcome measures, adjustment for multiplicity has been made using Bonferroni's adjustment and therefore a *p*-value of <0.025 will be considered statistically significant for each co-primary endpoint. 95% confidence intervals of comparative treatment effects will be reported.

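### The stated powers of 88% and 79% for treatment failure do not follow from section 19.2's own inputs, which give about 92-95% and 85-88%, and the sensitivity sentence names the wrong base rate

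*Protocol*

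**What the plan says.** Protocol section 19.2 fixes the treatment-failure calculation as follows.

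- Size and allocation: "800 patients randomised on a 1:1 basis to radical treatment or PA".
- Loss: "Allowing for a 10% total dropout rate across the entire study".
- Base rate: at the final analysis, "when we should have approximately 3 years median follow-up, we estimate that about 10" per cent of men having radical treatment will have failed. The comparison is 10% with radical treatment against 20% with partial ablation, hazard ratio 0.4722.
- Base-case power: these numbers "would provide approximately 88% power at p < 0.025".
- Higher-rate case: "approximately 79% power at p<0.025 to detect a difference of 15% versus 25" per cent, hazard ratio 0.5649.
- Lower-rate case: over 95% power for 5% versus 15%, hazard ratio 0.3156.
- Sensitivity sentence: "The statistical power would not be much affected if the failure rate in the radical treatment group was somewhat lower", or somewhat higher, than 15%.

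Section 19.4 names the log-rank test and explains the significance level: "adjustment for multiplicity has been made using Bonferroni's adjustment", hence 0.025 for each co-primary endpoint. It adds that "95% confidence intervals of comparative treatment effects will be reported". The sidedness of the test is not stated.

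**The concern.** Every input needed for a power calculation is printed in 19.2 or 19.4, and the failure rates are described as those reached by the final analysis. Expected events therefore follow directly, with no further accrual assumption. The printed powers are too low for those events, by more than rounding or choice of formula can explain. The next sentence then treats 15% as the reference rate, although 10% is the base case and 15% is its own higher-rate example.

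This is the power statement for a co-primary endpoint. A reader cannot tell which event count the design relies on: 108 and 144 from the stated inputs, or the smaller numbers that the printed powers imply.

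**Working it through.** **Inputs.** 400 per arm less 10% gives 360 per arm, 720 in total (19.2). Alpha is 0.025 (19.2, 19.4), taken as two-sided because it is half of 0.05 and two-sided intervals are planned; z = 2.2414. Rates are those at the final analysis (19.2). Counting dropouts as contributing no events is the cautious choice.

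**Hazard ratios.** ln(0.9)/ln(0.8) = 0.4722, ln(0.85)/ln(0.75) = 0.5649 and ln(0.95)/ln(0.85) = 0.3156. All three agree with the protocol.

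**Expected events**, 360 × (p1 + p2):
- 10% v 20%: 360 × 0.30 = 108
- 15% v 25%: 360 × 0.40 = 144
- 5% v 15%: 360 × 0.20 = 72

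**Formulas** (d events, n per arm, Δ the difference in rates, p̄ the mean rate):
- Schoenfeld: Φ(√(d/4)·|ln HR| − z)
- Freedman: Φ(√d·(1 − HR)/(1 + HR) − z)
- Two proportions: Φ([Δ√n − z√(2p̄(1 − p̄))]/√(p1(1 − p1) + p2(1 − p2)))
- With continuity correction: replace Δ by Δ − 1/n

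**10% v 20%**
- Schoenfeld: 5.196 × 0.7504 − 2.2414 = 1.658, so 95.1%
- Freedman: 10.392 × 0.3585 − 2.2414 = 1.485, so 93.1%
- Two proportions: (1.8974 − 1.1319)/0.5 = 1.531, so 93.7%
- Corrected: (1.8447 − 1.1319)/0.5 = 1.426, so 92.3%

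**15% v 25%**
- Schoenfeld: 6 × 0.5711 − 2.2414 = 1.185, so 88.2%
- Freedman: 12 × 0.2780 − 2.2414 = 1.095, so 86.3%
- Two proportions: (1.8974 − 1.2679)/0.5612 = 1.122, so 86.9%
- Corrected: (1.8447 − 1.2679)/0.5612 = 1.028, so 84.8%

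| Scenario | Events | Printed | Recomputed |
|---|---|---|---|
| 10% v 20% | 108 | 88% | 92.3-95.1% |
| 15% v 25% | 144 | 79% | 84.8-88.2% |
| 5% v 15% | 72 | over 95% | 98.4-99.6% |

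The gap is 92.3 − 88 = 4.3 to 95.1 − 88 = 7.1 points in the first row, and 84.8 − 79 = 5.8 to 88.2 − 79 = 9.2 points in the second. Working backwards, the printed 88% and 79% need about 83 and 114 events by Schoenfeld, or 91 and 120 by Freedman.

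**Readings that raise power further.**
- One-sided 0.025: 97.4% and 92.9% (Schoenfeld).
- Ignoring dropout: 96.9% and 91.5% (Schoenfeld).
- Reading the rates as 3-year rates, with 5-year accrual, 12 months' minimum follow-up and 10% dropout: 96-98% and 90-93%.

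**Readings that come near the printed figures**, each with an input that the protocol does not state:
- Alpha 0.0125: Freedman 89.0% and 79.9%.
- Alpha 0.01: two proportions 88.4% and 78.4%.
- 20% dropout with continuity correction: 88.5% and 79.6%.
- Rates read as 5-year rates, exponential failure, 5-year accrual and 12 months' minimum follow-up. With no dropout this gives 85 and 114 events, 89.0% and 79.2% by Schoenfeld. With 10% lost by 5 years it gives 82 and 110 events, 87.6% and 77.4%.

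**Sensitivity sentence.** The examples of 5% and 15% lie on either side of 10%, not of 15%. On the protocol's own figures, going from a 10% to a 15% radical-arm rate lowers power from 88% to 79%, so the type II error rises from 12% to 21%. The three printed values span at least 95 − 79 = 16 points.

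**The case against.** The best defence is that the printed powers come from an ordinary staggered-entry log-rank calculation using 5-year rates, and that only the time point went unstated. That reading does come close to both figures, so a deliberate and more cautious calculation cannot be ruled out. It is not what 19.2 describes, however. Under it only about 7% and 14% would have failed by the analysis (before dropout), whereas 19.2 puts radical-arm failure at about 10% by then. Section 19.2 also cites 15% to 25% failing within 5 years, not 10%. Because a smaller alpha or larger dropout fits about as well, the cause cannot be settled from the document.

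It is also fair to say that nothing operational depends on the figure. The stop-go criteria in 19.8 are recruitment counts, 19.7 plans no formal interim analysis, and 19.4 sets the primary analysis by calendar. A reader might infer that decisions about recruitment shortfall or data maturity rest on the stated power; the protocol gives it no such role.

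A reader might also infer that the two scenarios were swapped, since Schoenfeld gives 88% for 15% versus 25%. The other formulas give 85-87% there, and a swap would leave the 79% unexplained, so the match is best treated as coincidence. Nor is the missing event count a fault in itself, as that detail can sit in the SAP.

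Finally, whether power is little affected is partly a matter of wording, and the actual values follow in the next sentence. The 15% reference rate is not a matter of judgement.

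**Conclusion.** The point stands as an error of statement. On the inputs as written, power is about 92-95% rather than 88% for 10% versus 20%, and about 85-88% rather than 79% for 15% versus 25%. The claim of over 95% for 5% versus 15% is correct. This rests on two-sided 0.025, 720 evaluable men and failure rates that apply at the final analysis; a one-sided reading widens the gap.

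The error is conservative. A reader might infer that the trial is underpowered or that more men are needed; the recomputation shows the opposite for the stated inputs. What is established is that at least one input or figure in 19.2 is not as printed, not which one. The 15% base rate conflicts with the 10% base case on the face of the text, and the statement that power is little affected fits poorly with printed values from 79% to over 95%.

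**What to change.** In section 19.2, do one of two things:

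1. If the inputs are as written, restate the powers as about 92-95% (10% versus 20%, 108 expected events) and about 85-88% (15% versus 25%, 144 expected events), or as the single values from a named method.
2. If another calculation was used, state its actual inputs: the time point of the failure rates, accrual and follow-up, handling of dropout, alpha and sidedness. Give the matching event counts with the 10% dropout applied.

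In either case, change the reference rate in the sensitivity sentence from 15% to 10%, and replace the remark that power is little affected with the actual range across the three scenarios. Make the SAP agree. This is a text correction: the sample size remains 800 and no analysis changes.

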19.3 Choice of primary outcome

A co-primary end-point, incorporating treatment failure and HRQoL, has been chosen as this best reflects the relative trade-offs between potential oncological efficacy and functional outcomes between the two different treatment approaches of radical whole gland therapy versus PA.

19.4 Description of Statistical Methods

The primary analysis will be performed according to the Intention-To-Treat principle. Treatment failure will be compared between radical treatment and PA treatment using survival analysis techniques. Statistical significance between treatment groups will be assessed using log rank methods, and Kaplan-Meier survival curves will be used for graphical representation. Patients without treatment failure will be censored at time of death or time of last follow-up. Additional supporting analyses will be undertaken using Cox proportional hazards regression models adjusting for stratification factors and time from randomisation to start of treatment. Patients without treatment failure will be censored at their last known treatment failure free time.

For PORPUS and the other disease-specific HRQoL outcomes, Mixed Models for Repeated Measures (MMRM) will be used to evaluate differences over time by treatment group. MMRM models will be adjusted for treatment, baseline score, stratification factors, visit and a treatment by visit interaction as fixed effect terms, with patient included as a random effect. Differences between treatment groups will be reported as mean difference with 95% confidence intervals. Absolute and percentage average changes in HRQoL outcomes from baseline assessment will be displayed graphically. HRQoL forms that are returned partially complete will be analysed according to the scoring instructions for each questionnaire. The MMRM analyses will minimise the impact of missing data so the use of multiple imputation or other methods for dealing with missing data is not planned. Survival analysis techniques, as described for the treatment failure primary outcome, will also be used to compare differences between radical treatment and PA treatment for time to disease progression (including metastases), time to disease-specific mortality, and time to all-cause mortality. Patients without

disease progression at time of analysis will be censored at time of death or time of last known alive date.

The primary analysis is planned in the final six-months of the seven-year study, at which point median follow-up (from randomisation) will be approximately 3 years. To allow for having two co-primary outcome measures, adjustment for multiplicity has been made using Bonferroni's adjustment and therefore a *p*-value of <0.025 will be considered statistically significant for each co-primary endpoint. 95% confidence intervals of comparative treatment effects will be reported.

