Duration of	Participants will receive treatment	for their prostate cancer in	
intervention/treatment:	accordance with their randomised a	-	
	standard clinical care pathways. Tre	atment should commence within	
	12 months of randomisation.		
Follow-up duration:	Participants will be followed-up in the study for as long as the study		
·	remains open – for those recruited early in the study this may be for 5		
	years post-randomisation. The study team will also seek funding to see if longer term follow-up (up to 15 years post-randomisation) may		
	possible.		
	The minimum 'on study' follow-up for the last recruited patient is 12		
	months. All participants will continue NHS follow-up beyond the		
	duration of the study.	·····	
	Objective	Outcome Measure	
Co-primary objectives	To determine whether partial	Primary treatment failure (as	
and outcome measures:	ablation provides effective	defined in section 8.5)	
	oncological outcomes compared		
	with radical treatment		
	To determine whether partial	Health-related quality of life	
	ablation has a reduced side effect	(HRQoL) as measured by the	
	profile, and an improved patient-	Patient Oriented Prostate Utility	
	reported outcomes profile,	Scale (PORPUS-P).	
	compared with radical treatment		
Secondary objectives	Refer to the main OBJECTIVES AND OUTCOME MEASURES section of		
and outcome measures:	the protocol for full study objectives and outcome measures.		
and outcome medsures.			

ABBREVIATIONS

Adverse Event	
Chief Investigator	
Consolidated Standards of Reporting Trials	
Case Report Form	
Clinical Trials Unit	
Data and Safety Monitoring Committee	
Deep vein thrombosis	
Expanded Prostate Cancer Index Composite	
Good Clinical Practice	
General Practitioner	
Hospital Episode Statistics	
High Intensity Focal Ultrasound	
Health Research Authority	
Health-related Quality of Life	
Informed Consent Form	
Irreversible Electroporation	
Investigator Site File	
International Standard Randomised Controlled Trials Number	
Low Dose-Rate Brachytherapy	
Multi-disciplinary team	
Memorial Anxiety Scale for Prostate Cancer (MAX-PC)	
Medical Dictionary for Regulatory Activities	
Mixed Models for Repeated Measures	
Magnetic Resonance Imaging	
National Health Service	
National Institute for Health and Care Excellence	
National Institute for Health and Care Research	
Oxford Clinical Trials Research Unit	
Oxfordshire Prostate Cancer Support Group	
Partial Ablation	
Partial Ablation versus Radical Treatment	
Prostate Cancer	

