8.2 Primary objective and outcome measure

Objective	Outcome measure	Time point(s) of evaluation of this outcome measure (if applicable)
To determine whether partial ablation provides effective oncological outcomes compared with radical treatment	Primary treatment failure (as defined in section 8.5)	After a minimum of 3 years median follow-up post- randomisation, with at least 12 months post- randomisation follow-up of the last recruited participant
To determine whether partial ablation has a reduced side effect profile, and an improved patient-reported outcomes profile, compared with radical treatment	Health-Related Quality of Life (HRQoL) as measured by the Patient Oriented Prostate Utility Scale (PORPUS-P)	Baseline, 6wks post- treatment and 3mths, 6mths, 12mths post- randomisation, thereafter every 12 months until the end of the study.

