15.2 Randomisation procedure

Participants will be randomised by the local research team via a centralised validated computer randomisation program through a secure (encrypted) web-based service, RRAMP (https://rramp.octru.ox.ac.uk), provided by the Oxford Clinical Trials Research Unit (OCTRU), accessed via the PART REDCap study database.

Participants will be randomised in a 1:1 ratio to one of the following treatment arms:

Partial Ablation (intervention)	Participants will undergo partial ablation using either HIFU or IRE.
Radical Treatment (control arm)	Participants will undergo radical treatment by one of the following: 1) radical prostatectomy 2) radical radiotherapy 3) low dose-rate brachytherapy

Upon randomisation of a participant the central study office and a member of the local study team will be notified. This will take place via an automated email.

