16.5 Health-related quality of life questionnaire and health care use questionnaires

Health-related quality of life will be evaluated using validated questionnaires (PORPUS, IPSS, EQ-5D-5L, EPIC and MAX-PC (modified 18 item)) completed 6 weeks post-treatment and at 3 months, 6 months, 12 months post-randomisation and annually thereafter. Information about health care use will also be collected using a health care use questionnaire completed by study participants at the same time points, except 6 weeks.

Participants will be e-mailed a link to complete their study questionnaires electronically where possible (participants will be asked at their baseline visit whether they wish to complete follow-up questionnaires electronic or on paper with postal return). Paper questionnaires may also be used if requested. A health care use questionnaire will also be sent to participants at the same time points to identify and record items relating to utilisation of relevant health care resources. Where paper-based questionnaires are used, data will be entered into the study database by the local site research team.

Participants may be sent up to two reminder messages and/or where possible may be asked to complete questionnaires during a routine clinic visit. Participants that fail to complete study questionnaires may be telephoned by either the site research team or the central study team at the University of Oxford to collect the data or request return of the questionnaire.

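### PORPUS-P model: one baseline slope serves every visit; a baseline-by-visit term costs almost nothing, can sharpen per-visit contrasts and protects against baseline-dependent loss

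*Protocol*

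**What the plan says.** Protocol 19.4 names the fixed effects for PORPUS and the other disease-specific HRQoL outcomes: "MMRM models will be adjusted for treatment, baseline score, stratification factors, visit and a treatment by visit interaction as fixed effect terms". On the correlation within a man, the section says only that the model is fitted "with patient included as a random effect". Treatment is allowed to act differently at each visit; the baseline score is not. The same section relies on this model to deal with missing HRQoL data and plans no multiple imputation.

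The outcome table in 8.2 sets the PORPUS-P schedule as "Baseline, 6wks post- treatment and 3mths, 6mths, 12mths post- randomisation" and yearly after that. Section 16.5 agrees: forms are "completed 6 weeks post-treatment and at 3 months, 6 months, 12 months post-randomisation and annually thereafter". The synopsis (section 6) says that treatment should start within "12 months of randomisation". Section 9.2 makes collection at 24 and 36 months for all 800 men conditional on further funding. Section 19.1 leaves full analysis detail to the SAP.

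**The concern.** The visits are unlike one another. The 3- and 6-month forms, and for some men the 12-month form, are timed from randomisation and can be completed before any treatment; those scores should follow baseline closely. The 6-week form is timed from treatment, so it always falls in the acute phase. Later forms lie years from baseline. One slope for all of them assumes that baseline predicts the score equally well throughout, and the protocol gives no ground for that.

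Two things are at stake, both limited. Where the common slope is wrong for a visit, baseline variation stays in the residual and the treatment contrast at that visit is slightly less precise. And where responders at a visit differ in baseline between arms, the adjustment removes too much or too little of that difference, and the remainder enters the treatment estimate. The model serves a co-primary outcome and the other HRQoL scores.

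**Working it through.** **1. The plan's own figure.** Section 19.2 assumes "800 patients randomised (and 10% lost to follow-up in total across the study") and claims "over 90% power at p<0.01 to detect a small to moderate (0.3sd) effect size". Section 15.2 states that "Participants will be randomised in a 1:1 ratio", which gives 800 × 0.9 / 2 = 360 per arm. Taking the test as two-sided (the protocol does not say), 0.3 / √(2/360) = 4.02, and Φ(4.02 − 2.576) = 92.6%. At the co-primary level of 0.025 it is Φ(4.02 − 2.241) = 96.3%. The stated power reproduces, without any baseline adjustment.

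**2. Precision formula.** Let r be the correlation of baseline with the score at a visit (unit variances) and b the common slope. The residual variance is 1 − r² with a visit-specific slope and 1 − r² + (r − b)² with the common slope. The variance inflation is therefore 1 + (r − b)² / (1 − r²). The protocol gives no r, so every value below is assumed.

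**3. One uneven pattern, two covariance models.** With complete data and a correlation of 0.60 between follow-up visits, full visit-specific covariance gives b = 0.635. A random patient intercept, the natural reading of 19.4, gives b = the mean of r = 0.50.

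| Visit | Assumed r | Excess variance, b = 0.635 | Excess variance, b = 0.50 |
|---|---|---|---|
| 6 weeks | 0.35 | 9.3% | 2.6% |
| 3 months | 0.70 | 0.8% | 7.8% |
| 6 months | 0.60 | 0.2% | 1.6% |
| 12 months | 0.50 | 2.4% | 0.0% |
| 24 months | 0.45 | 4.3% | 0.3% |
| 36 months | 0.40 | 6.6% | 1.2% |

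For example, at 6 weeks (0.35 − 0.635)² / (1 − 0.35²) = 0.081 / 0.8775 = 9.3%, against (0.35 − 0.50)² / 0.8775 = 2.6%. At 3 months with b = 0.50, 0.20² / 0.51 = 7.8%.

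The flatter pattern 0.50, 0.60, 0.60, 0.50, 0.50, 0.45 under visit-specific covariance gives 0.3% to 1.3%.

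**4. Steadily falling correlations.** Here b is the mean of r and 360 men per arm are taken at every visit. The last two columns give power for 0.3 SD at p<0.01 at the visit where it is lowest.

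| r, first to last visit | Largest excess SE | Common slope | With interaction |
|---|---|---|---|
| 0.5 throughout | 0% | 98.1% | 98.1% |
| 0.65 to 0.45 | 0.9% | 97.2% | 97.3% |
| 0.75 to 0.35 | 4.5% | 94.8% | 95.7% |
| 0.80 to 0.20 (extreme) | 11.8% | 91.2% | 93.7% |

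An excess of 4.5% in SE is 1.045² − 1 = 9% in variance; the extreme 11.8%, at one visit only, is 25%.

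**5. Incomplete visits, loss unrelated to baseline.** Simulation: 800 men, six visits, unstructured covariance, 97% falling to 40% observed, 400 runs per pattern. Excess model SE was 0% (flat), at most 0.6% (0.65 to 0.45) and at most 2.9% (0.75 to 0.35). In the last case power at p<0.025 at the visit with 40% observed was 79% with the common slope and 82.5% with the interaction; other visits moved by about 0.5 points or less. Mean estimates were about 0.30 under both models.

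**6. Incomplete visits, loss depending on baseline in opposite directions by arm.** Simulation with the correlations of step 3, a true effect of 0.30 SD, unstructured covariance, about 39% missing at 24 and 36 months, a baseline difference among responders of about 0.5 SD (deliberately strong) and 60 runs: the common slope gave 0.26 and 0.23 at those visits; the interaction gave 0.30 and 0.30. A separate simulation that varied the strength gave about 0.27 to 0.29 under mild and 0.22 to 0.27 under strong differential loss with one slope, and about 0.30 with the interaction.

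**The case against.** The strongest reply is that nothing here is wrong. Baseline as a main effect is a standard adjustment, and with complete data randomisation keeps the treatment contrast unbiased whatever the slope. Section 19.1 says that the protocol only summarises the analysis, so the SAP could add the term. The correlations are assumed. Section 19.4 speaks of differences over time and names no single visit as the co-primary test; with complete data and a random intercept, a contrast averaged over visits loses nothing, because the common slope is then the mean of the visit slopes. Late data will also be missing partly because men were recruited late, which should not depend on baseline differently by arm.

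Most of this stands. It limits the point to an optional refinement, and it rules out two stronger readings. A reader might infer from the 9% at 6 weeks that the plan wastes the equivalent of some 60 of 720 men there. The documents do not support that: the figure needs assumed correlations and a visit-specific covariance, whereas under a random patient intercept the same correlations give 2.6% at 6 weeks (about 18 men) and move the largest loss to 3 months. A reader might also infer that the extra term is bound to sharpen the contrasts; with equal slopes it gains nothing.

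Two parts of the reply do not dispose of the point. Section 19.4 does list the model terms, so the protocol is the right place for the phrase. And unbiasedness through randomisation covers all randomised men, not those who still respond at 24 or 36 months.

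**Conclusion.** The point holds as a free improvement of low importance. The common slope is valid with complete data, and the stated HRQoL power is safe: in every pattern tried, power for 0.3 SD at p<0.01 stayed above 91% with 360 men per arm at each visit, before allowing for sparse late visits. Letting the slope vary gains nothing if slopes are equal and roughly 1% to 9% in variance at the worst-affected visit under mild to moderate differences; only the extreme pattern exceeds that. Which visit gains depends on the covariance model.

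The better reason for the term is protection. If loss at late visits depends on baseline differently by arm and the slope is wrong there, the estimate shifts, in the simulations by about 0.01 to 0.08 SD on a true 0.30. That matters somewhat because 19.4 relies on this model alone for missing HRQoL data. The documents do not show that such loss will occur. The baseline-to-visit correlations, the covariance between visits, the late-visit completeness and the loss mechanism are all assumptions.

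**What to change.** In Protocol 19.4, add *and a baseline score by visit interaction* to the fixed effects for PORPUS-P and the other HRQoL scores, and carry the same wording into the SAP. The cost is one phrase and about one parameter per additional visit: five with six follow-up visits, against some 720 men. Data collection and sample size do not change.
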